#### **Recruitment and Consent**

Participation in the study will be voluntary. We will rely on the schools, their Head teachers, local councils, community and church leaders, and local community development & healthcare workers to help with distribution of recruitment fliers. In addition, we will make use of the school academic calendar and recruit participants as they report/register for school. In most cases, participants entering senior 1 do come with their parents or caregivers to meet with the administration to register (normally occurs within the first 1-4 weeks of the academic term). School administrators will give each adolescent (and parent, for adolescents < age 17) a flyer that introduces the project and invites all the caregivers who may have a child eligible for the project to contact the school for details. In addition, Parish Priests, Local Council/village council leaders, local community development and healthcare workers will distribute flyers during their community visits (and at local council village meetings) to inform caregivers whose adolescents meet the inclusion criteria – and adolescents who may not yet have reported to school. Adolescents and caregivers who indicate interest will be invited to come to the school in-person for a one-on-one information meeting with the research team (in-country Co-Is ([name] and [name]) during which they will be given the details of the *Suubi4Her* project, and will be informed verbally and in writing that study participation is voluntary. They will also be

informed of the potential risks and benefits of participating in the program. [name] (the PI) will join the team during the recruitment and consent process, when in the country. We will obtain written informed consent from the caregiver for each study participant, and then in a separate step will obtain a written informed assent form from each adolescent who agrees to participate in the study. The research team will perform the consenting process during study recruitment, prior to the baseline assessment. The processes for adult caregivers and youth will be completely separate to avoid any coercion.

Given the research team's experience with the sets of economic empowerment studies informing this R01, we anticipate that most caregivers may not be English-speaking. For that reason, the caregivers' consent forms will be translated into Luganda (the local language spoken in the study area) from English, and then back-translated into English by a certified translator at a local University (Makerere, Nkozi or Mutesa Royal University, Dept. of Languages). The PI ([name]), the in-country Co-I ([name]) and the in-country Project Coordinator ([name]) are all fluent in Luganda. This will be helpful in cross-checking the translated documents.

Additionally, although all the children will be English-speaking (English is the official and instructional language used in schools in Uganda), some may be more comfortable using Luganda (local dialect). Therefore, the assent process will be conducted in English or Luganda (local language) depending on participants' English proficiency. Just like with the caregivers' consent forms, all adolescents' assent forms will be translated from English to Luganda and back-translated by a certified translator from a local university (Makerere, Nkozi or Mutesa 1 Royal University Department of Languages).

The PI, in-country Co-I ([name]), the in-country Project Coordinator ([name]), or research assistants will read and explain the consent form to the caregiver. In signing the consent form, the caregiver will be consenting to the adolescent's participation in the study screening and enrollment process (which will include having her blood drawn to ascertain HIV, urine testing to determine pregnancy, and high vaginal swab to establish the status on the three STIs to be tested Gonorrhea, Trichomonas and Chlamydia); recruitment and participation in the study (if inclusion criteria is met); and also authorizing access to the adolescent's school records by the Project Coordinator and/or the PI. Each adolescent will also go through the same process. They will each be read their assent forms before signing.

During the consent process, the Project Coordinator and either the PI ([name]) or Co-I ([name]) or research assistant will explain the study procedures to the caregivers. After the team (Project Coordinator and either PI or Co-I) is assured that the caregivers fully understand what would be expected of the adolescent and the caregiving family, the caregiver will be allowed to sign the consent form.

Adolescents will be consented separately from their caregivers. An adolescent to be included on the list of interested participants will sign a standard assent form. The Project Coordinator and either the PI ([name]) or Co-I ([name]) or research assistant will read and explain the form to the adolescent, and at the end of each section will solicit and answer any questions from the adolescent. During the consent process, the Project Coordinator or research assistant and either the PI ([name]) or Co-I ([name]) will explain the study procedures to the adolescents. After the Project Coordinator and either the PI or Co-I are assured that the adolescent fully understands what would be expected of her and the caregiving family, the adolescent would be allowed to sign the informed assent form.

In both the consent and assent forms, it will be clearly stated that the adolescent can withdraw from the study at any time, for any reason, with no explanation, and would not be penalized in any way. It will state that a participant may refuse to answer any questions at any time, may review any materials, may request that we erase any of their responses and may make inquiries and address complaints to Executive Secretary, Uganda National Council for Science and Technology, Chair of UVRI Research and ethics committee or Chair of the Washington University's Committee for the Protection of Human Subjects. As mentioned earlier, the research team will also inform the participant of any potential risks and benefits of participating in the program. Each participant will receive a copy of the assent/consent form, and both the adolescent minor and her caregiver will be thoroughly briefed regarding the importance of assent/consent being both informed and voluntary.

### **Potential Risks**

There are no major risks involved, however, an adolescent may feel embarrassed or uncomfortable during the recruitment and interview process when answering sensitive and personal questions, with urine collection for pregnancy testing, taking blood for HIV and/or high vaginal swabs for STIs (Gonorrhea, Trichomonas and Chlamydia). The process of blood draw may cause some discomfort, bleeding, or bruising where the needle enters the body, and in very rare cases, fainting or infection. First and foremost, interviewers will make it explicitly known to the participants that they may refuse to answer a question or decline to undergo a procedure, at any time. This will also be explained in writing on the consent/ assent forms. If an adolescent tells the interviewer that she is uncomfortable with a particular topic, that she prefers not to discuss a particular topic, or feels she cannot participate in the biomarker process the interviewer will move on to the next question/part of the interview.

Additionally, for questions measuring sensitive behaviors like sexual risk-taking and mental health, we will use audio computer-assisted self-interviews (ACASI) where the participant takes the survey herself on a mini laptop/iPad. This will provide additional privacy for the participant, can be programmed in multiple languages, and is designed for use by both literate and pre-literate populations. Research assistants will be available for any participant experiencing technical difficulty with the use of the computer-assisted interview.

To minimize risks in blood draw, blood will be collected very carefully by experienced clinicians from Rakai Health Sciences Program (RHSP). The PI, in country Co-I and Project Coordinator will also train all interviewers and research assistants on Good Clinical Practice (GCP) so that sensitive topics and issues are handled appropriately. In the event that a girl tests positive for HIV during the enrollment process, there is potential for emotional distress on the part of the participant and the family. In the event of a positive test, we will follow the established Uganda HIV disclosure guidelines provided by the Ugandan Ministry of Health, which require study participants to receive their HIV results independently, and then proceed to inform their parent or guardian, upon receipt of the child's consent to do so. The same protocol will be followed for girls who test positive on STIs (Gonorrhea, Trichomonas or Chlamydia) and those with a positive pregnancy test. Disclosure will be handled by trained medical personnel and social workers at Rakai Health Sciences Program (RHSP). The same process has been followed in several studies by RHSP. Girls found to be HIV positive will be referred for care and support to our extensive network of collaborating clinics in the study area. Girls who are pregnant will be linked to antenatal care services at an existing health facility of their choice (within the study area), and will thereafter be followed up by peer mothers for peer support. Those testing positive on any of the three STIs (Gonorrhea, Trichomonas or Chlamydia) will be linked to sexually transmitted infection treatment clinics offering adolescent-friendly services. As mentioned

earlier, study participants will receive their HIV results independently, and then proceed to inform their parent or guardian, upon receipt of the child's consent to do so. Research Assistants will contact girls who test positive 30 days after disclosing their status, to confirm that they have connected with follow up care and have access to comprehensive care services.

#### **Protection from Potential Safety/Clinical Risks**

The current study has instituted important safeguards to protect the welfare of study participants. The PI ([name]) and in-country Co-I ([name]) or designee will train the team members based in Uganda to identify risk factors associated with adverse events. For purposes of this study, adverse events include potential for suicide, homicide, worsening of participant physical health, new or escalating physical/emotional abuse occurring within families, or clinical worsening of participant mental health that may be related to the proposed preventative intervention. Staff members will be instructed that if any adverse event or risk for such event related to a child or adult caregiver involved with the study is identified, participant involvement will be halted immediately and the appropriate personnel contacted. Study staff will be informed of the protocol of rescue procedures in the occurrence of adverse events, which begins with the notification of the in-country Project Coordinator ([name], a Clinical Psychologist with extensive experience working in the same study regions in Uganda), at an emergency local Ugandan [contact]), and our collaborating Priest in-charge of schools in the study area ([name]) at an emergency local Ugandan number ([name]). The Project Co-Coordinator, [name], is a native Ugandan, trained in Clinical Psychology from South Eastern Louisiana University (Louisiana, USA). She has advanced clinical training in the delivery of human services, and she is knowledgeable about existing resources that can provide help and support to participants in the study that experience clinical emergencies or are in need of additional interventions that cannot be provided within the research study context. The other Project Co-Coordinator, [name] (at [name]) is a trained Teacher (Makerere University), and a Social Worker (MSW from Washington University, USA). Both [name] and [name] have extensive knowledge coordinating clinical trials. They have both worked on three projects whose preliminary findings and protocols guide this application (Suubi-Maka, Bridges and Suubi+Adherence). In addition, in the occurrence of adverse events, the two Project Coordinators will contact the in-country Co-I ([name]) immediately at an emergency number ([name]) and [name] ([name], if he is in the research study area) once emergency personnel in field have been notified. All study personnel must complete this training before they are permitted to administer any activities in the current study.

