## Suubi4Her Proposal

Final Version: 7-September-2017

**Study Overview.** The Suubi4Her program will test the effects of a combination asset-based financial inclusion intervention (YDAs) with an evidence-based family strengthening intervention to be delivered via multiple family groups (MFG) to understand the effects and costs associated with a combined intervention versus YDA alone. Specifically, the proposed study addresses three study aims:

**Aim 1.** Examine whether the *Suubi4Her* intervention is effective in protecting adolescent girls against known HIV risk factors (including economically-motivated sex and intimate partner violence).

**Aim 2.** Elucidate the effects of the *Suubi4Her* intervention on behavioral health functioning (i.e., depression, self-efficacy and hopelessness) and examine the effects of these variables as potential mechanisms of change, mediating the relationship between each intervention and HIV risk reduction.

**Aim 3.** Evaluate the cost-effectiveness of each intervention condition.

To address the three aims guiding the proposed study, we will randomize girls (at the school level) to one of three study conditions: 1) YDA condition with a 1:1 saving incentive match rate – for educational purposes and microenterprise development (n=420 participants; n=14 schools); 2) YDA + MFG intervention condition (n=420 participants; n=14 schools); 3) A control condition receiving standard health and sex education provided in schools (n=420 participants; n=14 schools). We detail the three study arms below.

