sent directly to the vendor with the required particulars of the participant). The accounts will be monitored by Drs. [name] (PI) and [name] (in-country Co-I), assisted by the project coordinator and financial manager in Uganda. Experience with our earlier studies indicates the accounts are easy to monitor through monthly bank statements. A participant's access to the matching funds is conditional upon completion of 12 financial management workshops over 12 months.

The matched savings accounts include financial management (FM) workshops and an IGA promotion component. The FM workshops, to be implemented by our collaborating community agency (RTY-Uganda) in collaboration with the financial institutions holding the YDAs, will consist of 12 general workshops that will: a) introduce participants to the notion of asset-building; b) cover asset-building strategies in detail, e.g., saving and investing in IGAs; c) cover specific topics related to saving, e.g., the importance of saving and how it can be done. There will also be asset-specific trainings following the general FM workshops.

**Combination Intervention: Youth Development Accounts (YDA) + Multiple Family Groups (MFG).** This arm is intended to directly address both the economic needs of the participating adolescent girls as well as their mental health functioning. This combination arm tests whether combining two evidence-based interventions will reduce HIV risk over and above a financial intervention (YDA) or usual care alone. The combined arm will consist of: a) a family monetary savings program using Youth Development Accounts (YDA) (detailed above), and b) a family-based dialogue and training via Multiple Family Groups (MFGs) focused on strengthening family relationships and mental health challenges which frequently accompany adolescent girls' transition to adulthood.

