Girls in the combination intervention group (YDA + MFG) will receive: 1) a monetary savings account in the form of a YDA, matched at a rate of 1:1. The YDA will operate exactly the same way as in a YDA-only group—detailed above; 2) in addition to the YDA, each girl will also be invited, together with her caregiving family, to attend 18 60-minute MFG sessions, over the course of 18 months, to be hosted within the community. The 18 sessions include an introductory session and a program evaluation session. Each session will involve 6-12 families. The MFG curriculum will incorporate broad conceptual categories targeting family-level issues and concerns that may impact families' abilities to incorporate new behaviors. Each session will provide numerous opportunities for family members to discuss the realities of family life, as well as perspectives on culture and values, specifically those related to gender. Content is intended to foster both within and between family interaction, learning and communication. Sessions will be facilitated by trained community-level Lay Counselors composed of priests, village health care workers and community extension workers. Training of Lay counselors and having them facilitate the MFG is intended to ensure intervention fidelity, and build capacity to sustain the intervention for the community at study end.

**Usual Care: Health and Sex Education and HIV Prevention Curriculum in Secondary Schools.** Two curriculums will be delivered in all our participating secondary schools: Life Planning Skills and Adolescent Sexual Reproductive Health. All enrolled participants, both in control and treatment conditions, will be exposed to these curriculums. Specifically, the content related to HIV and sexual risk-taking behaviors will include delaying sex; using condoms and contraception; preventing forced sex; and preventing substance abuse. This curriculum will also include education on gender equality. The content will primarily be delivered via lecture. Generally, Adolescent Sexual Reproductive Health content is and will be dispersed across a range of academic subjects in secondary schools. In each class, students tend to receive information about sexual activity, HIV prevention, and gender relevant topics. Prior to study

implementation, we will hold induction meetings for all teachers involved in the study to ensure uniform delivery of this bolstered usual care.

[figure not shown]

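### The mental-health adverse event is defined by its relation to the intervention, and events can be noticed at 3, 15 or 33 scheduled contacts by arm, so crude event counts are not comparable between arms

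*Combined protocol and SAP*

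**What the plan says.** The section Protection from Potential Safety/Clinical Risks gives an open list of adverse events: potential for suicide or homicide, worsening physical health, new or escalating abuse in the family, and "clinical worsening of participant mental health that may be related to the proposed preventative intervention". The closing condition most naturally attaches to the mental-health item, though the grammar would let it cover the whole list. Action follows "if any adverse event or risk for such event related to a child or adult caregiver involved with the study is identified"; then "participant involvement will be halted immediately and the appropriate personnel contacted". All study personnel must complete the training "before they are permitted to administer any activities in the current study".

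The arms differ in how often staff see a girl:

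- The third arm is "A control condition receiving standard health and sex education provided in schools". Under Usual Care, the same curricula go to all three arms.
- In both YDA arms, access to the matching funds is "conditional upon completion of 12 financial management workshops over 12 months". In addition, "There will also be asset-specific trainings following the general FM workshops"; their number is not given.
- The combination arm runs the savings account in the same way and adds "18 60-minute MFG sessions, over the course of 18 months".
- Every arm is assessed at baseline and at 12, 24 and 36 months (Assessments).

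Monitoring and Responding to Adverse Events sends possible unanticipated events to the IRBs, which decide whether to stop the protocol temporarily. It also provides for a quarterly look at preliminary outcome data.

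**The concern.** Two features make the event record depend on the arm. First, relatedness is part of what counts as an event, when it could be judged after the event is logged. The same decline in mental health fits the listed item in YDA or YDA+MFG and hardly fits it in control. Second, an event enters the record only once someone identifies it, and girls in the intervention arms meet staff far more often. Both push the same way, towards more recorded events under intervention.

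What is at stake is the reading of the safety record. Without a control rate collected in the same way, background events in this age group cannot be told apart from harm. An arm that truly lowers events could even record more of them. This matters most in the first year, because a girl's first post-baseline outcome is due only at month 12.

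**Working it through.** **Contacts.** The documents state no contact total or event rate, so there is no figure of theirs to reproduce. Scheduled post-baseline contacts per girl are:

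- Control: 4 assessments − baseline = 3
- YDA: 3 + 12 workshops = 15
- YDA+MFG: 3 + 12 + 18 sessions = 33

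The ratio is 1 : 5 : 11. The last two totals are minimums, because the asset-specific trainings are not counted.

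**From contacts to recorded events.** Contacts are not detections, so assumptions are needed. Suppose true event rates are equal in all arms. Let onset be uniform over 36 months and let an event last D months. Workshops fall monthly in months 1-12, MFG sessions monthly in months 1-18, and interviews at 12, 24 and 36. Each contact during the event finds it with probability p. Then

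share recorded = 1 − average over onset of the product of (1 − p) across contacts falling within the event.

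For control with D up to 12, at most one interview falls within an event, so the share is (3 × D / 36) × p(interview). With D = 6 and p = .3 this is (18/36) × .3 = .15.

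The grid was D = 3, 6 or 12; MFG detection .1 or .3; workshop detection 0 or equal to MFG; interview detection .3, .6 or .9. That makes 36 combinations. Selected rows:

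| D | MFG | Workshop | Interview | Control | YDA | YDA+MFG | YDA / control | YDA+MFG / control |
|---|---|---|---|---|---|---|---|---|
| 3 | .3 | .3 | .3 | .075 | .268 | .439 | 3.57 | 5.86 |
| 6 | .3 | .3 | .3 | .150 | .374 | .536 | 2.49 | 3.57 |
| 6 | .3 | 0 | .3 | .150 | .150 | .509 | 1.00 | 3.40 |
| 6 | .3 | 0 | .6 | .300 | .300 | .615 | 1.00 | 2.05 |
| 6 | .3 | 0 | .9 | .450 | .450 | .721 | 1.00 | 1.60 |
| 12 | .1 | 0 | .9 | .900 | .900 | .927 | 1.00 | 1.03 |

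Over the whole grid the ratio to control is 1.0 to 3.6 for YDA (1.0 whenever workshops find nothing) and 1.03 to 5.9 for YDA+MFG. These figures cover unequal contact only; the relatedness condition would add to them.

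**Can a protective arm look worse?** Take 420 girls per arm and assume that YDA+MFG halves the true risk from 10% to 5%, with D = 6, MFG detection .3 and workshops 0:

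- Interview .3: control 420 × .10 × .150 = 6.3; YDA+MFG 420 × .05 × .509 = 10.7
- Interview .6: 420 × .10 × .300 = 12.6; 420 × .05 × .615 = 12.9
- Interview .9: 420 × .10 × .450 = 18.9; 420 × .05 × .721 = 15.1

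The order is reversed in 17 of the 36 combinations, some of them barely. Interview detection matters most, and the documents leave it unclear. Potential Risks puts mental-health questions on self-completed ACASI. Assessments gives only sexual risk as its example of ACASI content and has interviewers ask the non-sensitive questions.

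**After the fix.** Counting only what is found at the three shared assessments gives 3 : 3 : 3 opportunities.

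**The case against.** The strongest reply is that no planned analysis is harmed, and this stands. No section tests events by arm, and the IRBs are sent individual possible unanticipated events, with no mention of arm totals. The section on monitoring also says that reporting follows a project protocol, which is not shown; it may already separate relatedness from occurrence. The list is open, a possible relation is a low bar, and the other listed events apply in control if the condition covers only the last item. The enhanced usual care might be read as part of the intervention. No section says that workshops or MFG sessions screen for events; the training rule only makes noticing them possible, and only for staff who count as study personnel. None of this supplies an arm-neutral definition or a common method of finding events in the documents as they stand.

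Four stronger readings are tempting and are not supported:

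- *The safety sections contradict each other.* They do not. Training staff to spot any threat to welfare is broader than the event definition, but compatible with it.
- *Event reports are the only safety information in the first year, with no control contact.* Too absolute. Girls testing positive are contacted at 30 days and pregnant girls are followed by peer mothers, with no limit by arm. These girls are a subset only.
- *A protective arm will look harmful.* This holds in about half of an assumed grid and disappears in the worked example once interviews find 90%.
- *Halting biases the Aim 2 comparisons.* This would require that halted girls go unassessed and that halting, or its timing, differs by arm. The plan says neither.

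**Conclusion.** The point holds as a weakness of definition and record-keeping. The wording ties one listed event to the intervention, and scheduled opportunities to notice any event are at least 3, 15 and 33 by arm. Crude counts are therefore not comparable, and the record lacks a like-for-like control rate. The contact totals follow directly from the documents. The size of the distortion does not: recorded ratios of about 1.0-3.6 (YDA) and 1.03-5.9 (YDA+MFG) rest on assumed durations and detection probabilities, and fall to near 1 when events are long and interviews find most of them. No planned hypothesis test is shown to be affected. The correction is worth making because it is nearly free, and the unseen reporting protocol may already contain part of it.

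**What to change.** 1. Define and log each listed event in all three arms without reference to the intervention. Record judged relatedness, and place of detection (assessment or session), as separate fields.
2. Base any between-arm statement on events found at the shared 12, 24 and 36-month assessments, and list session-found events separately by arm. State that this gives no comparable signal for the first year. The comparison is even only if girls with a session-found event are still asked the same questions at assessments.
3. As a clarification only, reconcile the statement that involvement is halted with the follow-up described under Assessments and Study Population and with voluntary withdrawal under Recruitment and Consent. The text does not say whether scheduled assessments continue. The safety response itself is for the sponsor.

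If the project protocol already does this, a cross-reference is enough. Cost: a few sentences, two form fields and one table; no extra visits.
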